### 8.2.7.2 Exploratory Efficacy Analyses

One exploratory endpoint is the time to progression to probable AD dementia as determined by investigator-diagnosis (noting that the formal adjudication process utilized in the initial 104-week study, will not be utilized in the long-term safety study). All available data from the initial 104-week trial will be utilized in the analysis. A Cox proportional hazard model adjusting for APOE4 genotype (APOE4 positive, APOE4 negative), gender, geographic region, and the use of acetylcholinesterase inhibitors at screening (Use, Do Not Use) as categorical terms, with age and baseline MMSE score as continuous covariates will be used to compare the hazard functions of the 40 mg/40 mg arm to the Pbo/40 mg arm, as well as to compute the hazard ratios and the corresponding confidence intervals (CIs). Subjects who reach the maximum treatment duration will be considered as completers and will be censored at that timepoint.

The 12 mg/12 mg arm will be compared to the Pbo/40 mg arm in a similar fashion.

If the analysis model fails to converge due to the presence of too many factors in the model (i.e., empty cells), then factors will be removed one at a time until the model does converge. Factors will be removed in the following order: geographic region, gender, use of acetylcholinesterase inhibitors at screening, and APOE4 genotype.

For all other continuous exploratory endpoints, the same model that is used for the primary endpoint will be used as were specified in Section 8.2.3.1.

No sensitivity analyses will be conducted on any of the exploratory endpoints.

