### **8.2.7 Statistical Methods for Efficacy Analyses**

#### **8.2.7.1 Primary Efficacy Analysis**

The primary efficacy endpoint is the change from Baseline (CFB) in CDR-SB score at Week 130. Basic summary statistics (means and standard deviations, as observed), will be calculated.

A delayed start design will be used to support the potential disease modifying effect of MK-8931 by comparing the 40 mg/40 mg arm to the Pbo/40 mg arm. However, due to increased variance and anticipated dropout rate over time, the study is not powered to demonstrate significance on these endpoints, even if significance was demonstrated at 24 months in the initial study.

The 12 mg/12 mg arm will be compared to the Pbo/40 mg arm in a similar fashion.

All available data from the initial 104-week trial will be utilized in the analyses, even that from subjects who do not continue into long term trial. It is possible that the 40 mg dose may be dropped for reasons due to safety, in which case all subjects would receive 12 mg. The primary comparison in this case would be between the 12 mg / 12 mg arm and the Pbo / 12 mg arm (with any subjects receiving 40 mg excluded from the analysis).

A longitudinal ANCOVA model will be used on the change scores, with time treated as a categorical variable so as not to impose any restriction on the trajectory of the means over time. The analysis model includes treatment, time, the time-by-treatment interaction, APOE4 genotype (APOE4 positive, APOE4 negative), gender, geographic region, and the use of acetylcholinesterase inhibitors at screening (Use, Do Not Use) as categorical terms, with age and baseline MMSE score as continuous covariates. The baseline value of the dependent

variable, as well as the baseline-by-time interaction term will also be included. Model-based estimates of the mean change scores and the mean treatment difference on the change scores will be provided, along with the corresponding confidence intervals and p-values for the mean treatment differences. An unstructured covariance matrix will be used to model the correlation among repeated measurements.

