### 8.2.11 Sample Size and Power Calculations

#### 8.2.11.1 Sample Size and Power for Efficacy Analyses

##### 8.2.11.1.1 Parameter Estimates

Parameter estimates for the primary endpoint were obtained from the Alzheimer's Disease Neuroimaging Initiative (ADNI). Extrapolations out to 30 months (Week 130) were performed on the 24-month (Week 104) parameter assumptions used in the initial 104-week trial and these extrapolations are presented below in [Table 8](#).

Table 8 Parameter Assumptions for CDR-SB

Endpoint	Baseline SD	30m SD	30m CFB Mean (130-Week Placebo/ MK-8931 40 mg Progression Rate)	Corr(Base, 30m)
CDR-SB	0.86	3.05	2.13	0.359

Based on N=151 subjects from ADNI, Late MCIs with either CSF+ ( $\tau\text{au}/\text{ab142} \geq 0.39$ ) or PET+ ( $\text{pib} > 1.6$ ), and MMSE  $\geq 24$ .

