### 8.2.11.1.2 Power Calculations

Power calculations for the change-from-baseline treatment difference at 30 months (Week 130) were performed (via simulation) for CDR-SB even though there are no formal hypotheses for the endpoint in the long term trial. As shown in Table 9 the hypothesis is underpowered at Week 130, both marginally and when applying an informal sequential testing approach. Specifically, it is possible that formal statistical significance may be observed in the initial 104 week trial (under the prespecified multiplicity approach), while nominal marginal significance (ie, p-value < 0.02495) fails to be observed at Week 130, even if the true underlying effect of MK-8931 continues to increase. This is due to the assumed increased variance and dropout rate over time, with 90% of subjects who complete the base study assumed to continue on into the extension.

Table 9 Power Calculations (MK-8931 40 mg / MK-8931 40 mg vs. Placebo / MK-8931 40 mg)

Marginal Probability †	(%)
CDR-SB at Week 130	73.9
Sequential Probability	
Success ‡ for CDR-SB at Week 104 and CDR-SB at Week 130	73.4
Conditional Probability	
Success ‡ for CDR-SB at Week 130 given success on CDR-SB at Week 104	76.1
† Marginal power calculations at Week 130 do not require success at Week 104. ‡ 40 mg dose only Calculations are based on N=1350 randomized (450 subjects/arm) incorporating the assumed dropout rate of 25% at Week 104 and 37% at Week 130 ( $\alpha = 0.02495$ ).	

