### 8.2.12 Subgroup Analyses and Effect of Baseline Factors

Subgroup analyses will be conducted on CDR-SB, CCS-3D, ADCS-ADLMCI at Week 130. The consistency of treatment effect across various subgroups will be assessed through the computation of within group summary statistics (model-based and as-observed), along with nominal 95% CIs. Further, model-based between-group treatment differences (or hazard ratios, as appropriate) and the corresponding 95% CIs will be constructed for those comparisons (active/active vs. placebo/active), for which both treatment groups within the subgroup level have at least 75 subjects (roughly 15% of subjects randomized). No formal statistical testing of the treatment by subgroup interactions will be performed. The following subgroups will be examined:

- Gender (Male, Female);
- Age (< 65, ≥ 65 years of age);
- Race (white, black, Asian, other);
- Ethnicity (Hispanic, Not Hispanic);

- Geographic Region (US/Canada, Europe/Australia/New Zealand, Japan, Rest of World);
- APOE Genotype (APOE 4 positive, APOE 4 negative);
- Disease Severity via MMSE at Screening (24-26, 27-30)
- PET/CSF status at Screening (PET+/CSF+, PET+/CSF-, PET+/CSF Unknown, PET-/CSF+)
- CSF evaluation at Screening (CSF evaluated, CSF not evaluated)
- AD Treatment at Screening (use of AChEI or memantine, no use of AChEI or memantine)
- Vitamin E use at Screening (0-400 IU/day, >400 IU/day)

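### Baseline CDR-SB is not in the Cox model for time to AD dementia; adding it before unblinding costs almost nothing and may recover some power

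*Combined protocol and SAP*

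**What the plan says.** Section 8.2.7.2 specifies "A Cox proportional hazard model adjusting for APOE4 genotype (APOE4 positive, APOE4 negative), gender, geographic region" and AChEI use at screening, "with age and baseline MMSE score as continuous covariates will be used to compare the hazard functions of the 40 mg/40 mg arm" with those of the placebo/40 mg arm. The 12 mg/12 mg comparison is handled the same way. If the model does not converge, region, gender, AChEI use and APOE4 are removed in that order. The section also states: "No sensitivity analyses will be conducted on any of the exploratory endpoints".

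The primary CDR-SB model in section 8.2.7.1 has the same six covariates. There, the baseline value of the outcome, "as well as the baseline-by-time interaction term will also be included".

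Time to dementia is one of the exploratory objectives in section 3.3, and section 4.2.2.1 expects it to be informative to patients and physicians. Section 8.1.1 states that the trial has no formal hypotheses, and section 8.1.3 that there are no sample size calculations for the extension.

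**The concern.** In a proportional hazards model, leaving out a baseline variable that predicts the event pulls a non-null treatment hazard ratio toward 1, even under perfect randomisation, and costs power. Baseline CDR-SB is a natural candidate. It is the baseline of the trial's primary outcome measure, and section 8.2.3.1.2 shows that half of its boxes are functional (hobbies and home life, self-care, community affairs). Section 7.1.2.3.10 describes MMSE as a cognitive measure only.

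The continuous exploratory endpoints use the primary model and so are adjusted for their own baseline. Time to dementia has no baseline of its own, and nothing stands in for one. With no sensitivity analysis planned, no other analysis would show what the omission costs.

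**Working it through.** **Plan's own figure.** There is none to reproduce. The plan gives no hazard ratio, event count or power for this analysis. Table 9 concerns CDR-SB at Week 130, not time to dementia.

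**Inputs from the plan**
- Table 8: "CDR-SB 0.86 3.05 2.13 0.359", that is, baseline SD, 30-month SD, 30-month mean change, and correlation of baseline with 30 months.
- Table 9 footnote: "Calculations are based on N=1350 randomized (450 subjects/arm) incorporating the assumed dropout rate of 25% at Week 104 and 37% at Week 130".
- Level, section 8.2.11.1.2: "nominal marginal significance (ie, p-value < 0.02495) fails to be observed at Week 130". I take 0.02495 as two-sided. The 97.51% intervals in section 8.2.10 agree with that (1 − 0.9751 = 0.0249).

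**Inputs assumed, not in the plan**
- True conditional hazard ratio 0.70, constant over time.
- Control incidence of dementia at Week 104 of 20% or 35%.
- Follow-up to Week 130 or Week 364.
- Hazard ratio per SD of baseline CDR-SB, beyond the covariates already in the model, of 1.2, 1.4, 1.64 or 2.0.

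**Where 1.64 comes from.** R² = 0.359² = 0.129. On a complementary log-log scale the residual variance is π²/6 = 1.645, so the log hazard ratio per SD is √(0.129/0.871 × 1.645) = 0.493, and exp(0.493) = 1.64. This is a rough anchor. It uses the correlation with the 30-month *level* and makes no allowance for MMSE or the other covariates.

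The correlation with *change* is much smaller. Reading both Table 8 SDs as SDs of the score:
- covariance with change = 0.359 × 0.86 × 3.05 − 0.86² = 0.942 − 0.740 = 0.202;
- SD of change = √(0.86² + 3.05² − 2 × 0.942) = 2.86;
- correlation = 0.202/(0.86 × 2.86) = 0.08, so R² is about 0.7%.

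A dementia diagnosis reflects the subject's state, so level is probably the better guide. Neither figure is a hazard ratio for diagnosed dementia.

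**Simulation.** 1,000 runs per scenario, 450 per arm, exponential event times, and exponential dropout reaching 25% at Week 104. Cox models were fitted with and without the covariate and tested at two-sided 0.02495. The four settings, in order:
- A: 20% incidence, Week 130, about 160 events.
- B: 20%, Week 364, 274–287 events.
- C: 35%, Week 130, about 280 events.
- D: 35%, Week 364, 424–447 events.

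| HR per SD | Treatment HR, omitted (A, B, C, D) | Treatment HR, included | Power %, omitted → included | Loss (points) |
|---|---|---|---|---|
| 1.2 | 0.699, 0.705, 0.700, 0.700 | 0.698, 0.702, 0.698, 0.696 | 48.5→48.0, 77.6→77.6, 78.3→78.5, 94.4→94.9 | −0.5 to 0.5 |
| 1.4 | 0.700, 0.706, 0.705, 0.711 | 0.696, 0.698, 0.699, 0.701 | 49.4→50.6, 75.1→78.4, 77.2→78.9, 90.2→92.8 | 1.2 to 3.3 |
| 1.64 | 0.713, 0.711, 0.717, 0.722 | 0.705, 0.696, 0.705, 0.699 | 45.5→48.1, 70.5→76.0, 68.9→74.7, 86.8→93.1 | 2.6 to 6.3 |
| 2.0 | 0.717, 0.727, 0.726, 0.731 | 0.702, 0.702, 0.702, 0.696 | 41.1→48.2, 64.8→75.0, 66.3→75.6, 84.0→92.9 | 7.1 to 10.2 |

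The shift in the treatment hazard ratio is 0.001–0.004, 0.004–0.010, 0.008–0.023 and 0.015–0.035 for the four strengths.

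**Under the null** (true hazard ratio 1.0, setting C), omitted and included estimates are 1.002 and 1.002 at 1.64 per SD, and 1.004 and 1.006 at 2.0. Rejection rates are 2.9% and 2.7%, then 2.1% and 2.4%, against a nominal 2.5%.

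**Limits.** Each power estimate has a Monte Carlo standard error of up to √(0.25/1000) = 1.6 points; the paired difference is tighter. The simulated dropout is 1 − 0.75^(130/104) = 30% at Week 130, against the plan's 37%. A constant 0.70 to Week 364 ignores the placebo arm's switch to active drug at Week 104, so the Week 364 rows are illustrative.

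**The case against.** The case for leaving the model alone has real force.

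- **Severity is already adjusted for.** A reader might infer that the model ignores disease severity. It does not: section 8.2.12 lists "Disease Severity via MMSE at Screening (24-26, 27-30" as the severity subgroup, and baseline MMSE is in the Cox model. What is missing is a second measure with functional content. This stands.
- **There is no contradiction with the primary model.** A reader might infer one. CDR-SB enters the primary model as the baseline of its own outcome, and a time-to-event endpoint has no such baseline. The Full Analysis Set rule in section 8.2.4.1 is also specific to each endpoint, so it does not require baseline CDR-SB here. This stands.
- **The hazard ratio is not invalid.** A reader might infer bias. The shift is non-collapsibility: without the covariate, the model estimates a less conditional hazard ratio, with no bias under the null. This stands.
- **Table 8 does not establish the size.** The 0.359 is unadjusted and refers to the 30-month level. Overlap with MMSE would shrink the loss, possibly to almost nothing. This stands.
- **No stated property is broken.** The endpoint is exploratory, with no power target. This lowers the priority.

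None of this shows that the plan already covers the point, or that adding the covariate has a material cost.

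**Conclusion.** The omission is a fact, and its direction follows if baseline CDR-SB predicts dementia beyond the six listed covariates. The size is uncertain. It runs from negligible at 1.2 to 1.4 per SD to 7–10 points of power at 2.0. At the Table 8 anchor of 1.64 it is about 3–6 points, likely an upper guide for that anchor because it precedes adjustment for MMSE. All of these figures rest on the assumed hazard ratio of 0.70, the assumed incidences and a constant effect.

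This is a free improvement of low priority. It is not an error that threatens the trial's conclusions, and the documents do not support saying that the planned analysis necessarily understates the effect by a known amount.

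**What to change.** In section 8.2.7.2, add baseline CDR-SB (from the initial 104-week trial) as a continuous covariate in the Cox model for both the 40 mg/40 mg and 12 mg/12 mg comparisons with placebo/40 mg. If the sponsor prefers not to, one sentence should give the reason.

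Make the change before the sponsor is unblinded on completion of the initial trial (section 8.1.4). Section 4.2.1.2 describes that trial as still ongoing, so the covariate can still be prespecified; added later, it could look data-driven.

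The non-convergence rule needs no edit, because it lists only categorical factors. The cost is one line of text and no new data. The one downside is that a subject without a baseline CDR-SB would drop out of the Cox model; the SAP should report how many do.

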### **8.2.7.3 Health Economic Endpoints**

The Modified RUD Lite will be evaluated by tabulating the counts and percentages of each living-arrangement category across the treatment arms and visits.

For HEA, the counts and percentages of each category of non-trial medical visit will be tabulated by treatment group and visit.

The EuroQoL Five Dimension Questionnaire (EQ-5D) will be evaluated by tabulating the counts and percentages of each health dimension by treatment group and visit. Basic summary statistics will also be computed for the assessment of subject health state (0-100 scale) by treatment and visit.

### **8.2.7.4 Pharmacogenetic Analyses**

The relationship between APOE genotype and the following clinical outcomes: CDR-SB, ADAS-Cog and ADCS-ADLMCI will be evaluated as an exploratory analysis.

Additional exploratory pharmacogenetics (PGt) studies may be performed if significant Pharmacokinetic/Pharmacodynamic (PK/PD) relationships are observed or for certain adverse events. Genomic markers of disease may also be investigated. Pharmacogenetic studies may use PK/PD results or clinical outcomes. Any nominally significant PGt relationships to outcome will require validation in future clinical trials.

### **8.2.7.5 Accounting for Missing Data**

It is expected that Missing at Random and Missing Completely at Random (MAR/MCAR) mechanisms will underlie most of the missingness. Reasons for discontinuation from the study may include lack of efficacy, adverse experiences, relocation, withdrawal of consent, protocol violations, and/or data processing issues. Missing data caused by relocation and data processing issues are likely to be MCAR. On the other hand, missing data caused by discontinuation due to lack of efficacy may belong to MAR because the discontinuation may depend on the observed efficacy outcomes. The MAR or MNAR mechanisms might each underlie the other reasons to some extent. If treatment in large part determines the loss of data for these other reasons (such as clinical or laboratory adverse experiences), the mechanism may be close to MAR because treatment assignment is an observed variable and included in the analysis model. Based on results from similarly-designed, previously-conducted trials, missing data due to other reasons is relatively infrequent. Of note, in the event that there are no missing data, the estimated treatment difference from the above cLDA model will be identical to that from a traditional longitudinal ANCOVA model which uses the baseline value as a covariate.

A pattern-mixture model based on the tipping-point approach will be used to assess the robustness of the primary analysis approach. For a given constant,  $c$ , the tipping point analysis is conducted in a fashion similar to that used in standard multiple imputation [29; 30; 31], whereby  $m$  complete datasets are randomly generated using the original observed dataset. These  $m$  complete datasets are subsequently analyzed using the primary model, and the results of those analyses are then combined. The construction and analysis of these  $m$  ( $=50$ ) datasets requires four primary steps:

- a. Using a Markov Chain Monte Carlo method [32], make the observed dataset monotone-missing. This will be accomplished for each treatment group using “PROC MI” within SAS 9.3 by utilizing the options “mcmc chain=multiple impute=monotone;”, in conjunction with all of the covariates (excluding treatment) included in the primary analysis model. The random seed will be set equal to 8931019. This step will generate  $m$  monotone-missing datasets.
- b. Applying parametric regression to the monotone-missing datasets, impute the missing values in a stepwise fashion starting with the first postdose timepoint. This will be accomplished for each treatment group using “PROC MI” within SAS 9.3 utilizing the option “monotone reg”, in conjunction with all of the covariates (excluding treatment) included in the primary analysis model. The random seed will be set equal to 8931019. This step will generate  $m$  complete datasets.
- c. To implement the tipping-point aspect of the procedure, subtract a constant  $c$  from each of the imputed values of the active arms (to the detriment of active).
- d. Analyze each of the post-imputation complete datasets using the primary model, obtaining point estimates for the mean of interest (e.g., change-from-baseline treatment difference at 104 weeks) and the associated variance.

Using “proc mianalyze” within SAS 9.3, the  $m=50$  means and variances from the  $m$  analyses will be combined to obtain the final test statistic and p-value [29]. The final test statistic  $\bar{Q} / (T^{(1/2)})$  is approximately distributed as  $t_v$ , where  $\bar{Q}$  is the sample mean of the  $m$  mean estimates,  $T = \bar{U} + (m+1) (B/m)$ ,  $\bar{U}$  is the sample mean of the  $m$  variance estimates, and  $B$  is the sample variance of the  $m$  mean estimates. The degrees of freedom,  $v$ , will be computed as follows [33],  $v = [(v_1)^{-1} + (v_2)^{-1}]^{-1}$ , where  $v_1 = (m-1) [1 + (\bar{U}/(1+m^{-1}) B)]^2$  and  $v_2 = (1-\gamma) v_0 (v_0 + 1) / (v_0 + 3)$ , with  $\gamma = (1+m^{-1}) B / T$  and where  $v_0$  represents the complete-data degrees of freedom.

This procedure will be repeated (using the same  $m$  imputed datasets) until the smallest  $c$  is found such that the “significant” result turns “non-significant” (i.e.,  $p \geq 0.02495$ ). This tipping point value  $c$  provides a measure of robustness of the primary result. A relatively large value of  $c$  implies better robustness of the primary analysis against the impact of missing data in the study. It is noted that when  $c=0$  the tipping point analysis described above corresponds to an analysis conducted under the assumption that the missing data are MAR. For values of  $c$  larger than 0, the tipping point analyses do not assume that the missing values follow a MAR mechanism. In fact, the analysis is based on a special MNAR mechanism in which all missing data in the active arm are assumed to have a worse response

by a constant amount of  $c$  than the values would have had under MAR, while the missing data in the control group are assumed to be the same as that obtained under MAR.

It may be necessary to adjust  $c$ , in order to calibrate between the two analysis approaches (ANCOVA vs. MI), should a value of  $c=0$  yield a different p-value than is produced from the primary ANCOVA analysis model. This will be accomplished by subtracting the calibration value  $c_{prim}$  from  $c$ , where  $c_{prim}$  is the offset to be applied to the active arm, per the above MI approach, that will yield the same p-value as produced by the primary ANCOVA analysis.

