## **2.0 TRIAL DESIGN**

### **2.1 Trial Design**

This is a long-term safety and efficacy study (up to 260 weeks) which will be available to subjects who have completed the initial 104-week trial of MK-8931-019.

The initial 104-week trial is a double blind, randomized, parallel group, placebo controlled, multicenter trial in subjects with amnesic mild cognitive impairment (aMCI) due to Alzheimer's Disease (AD), referred to herein as prodromal AD. The initial 104-week trial, detailed in a separate amendment, includes two active dose arms of MK-8931 (12 mg and 40 mg) and placebo. Duration of treatment is 104 weeks (24 months). MK-8931 is a potent  $\beta$ -site APP cleaving enzyme 1 (BACE1) inhibitor being developed for the treatment of AD. The initial 104-week trial will enroll subjects who meet criteria for prodromal AD, which is defined as subjects who have aMCI and are positive for an AD biomarker. The primary AD biomarker to be used for the inclusion criterion is cortical amyloid load measured with positron emission tomography (PET).

At the end of the 104-week trial, subjects who have completed treatment and satisfy eligibility criteria may choose to participate in this trial, during which all subjects who received placebo during the initial 104-week trial will receive active drug. Subjects who progress to dementia due to AD in the main 104 week study will not be permitted to move into the long term extension study.

This trial will start with enrollment of the first subject who completes the initial 104-week trial and chooses to participate in the long term trial. The long term safety and efficacy trial will end 5 years after the first subject enrolls (260 weeks), or a) when the drug either becomes commercially available (locally), or b) when the MK-8931 program is terminated (whichever comes first). The duration of the trial may be even shorter for subjects in particular regions, per local regulation.

Specific procedures to be performed during the trial, as well as their prescribed times and associated visit windows, are outlined in the Trial Flow Chart - Section 6.0. Details of each procedure are provided in Section 7.0 – Trial Procedures.

This trial will use an independent, external Data Monitoring Committee (eDMC) to monitor safety at the appropriate frequency and for the duration required per the eDMC Charter.

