#### **4.2.1.2 Rationale for Subject Population and Dose**

The recent results from Protocol 017 indicate that MK-8931 is not effective when treatment is initiated in subjects with mild/moderate AD. The amyloid hypothesis suggests, however, that earlier treatment with a BACE inhibitor (prior to the onset of dementia) could be beneficial even if ineffective at later stages. The initial 104-week trial of Protocol 019 in prodromal AD is still ongoing so the impact of BACE inhibition in this earlier stage of the disease is not yet known. Given this uncertainty along with the 017 results, subjects who tolerated study medication, have not progressed to dementia and completed the initial 104-week trial of Protocol 019 may enroll in this long term trial. However, subjects who have progressed to dementia will be excluded since the 017 results indicate increased adverse events in addition to no efficacy.

Subjects in the initial 104 week trial who progress to dementia during that time have a 2 out of 3 chance of being on active treatment with MK-8931. Based on the view that these subjects could still benefit from MK-8931 since it was initiated before the onset of dementia, one alternative is to allow these subjects into the extension trial. However, since the blind will be maintained in the extension, it is not possible to include these subjects while excluding subjects who were on placebo during the initial 104-week trial. Given the concern that the placebo treated subjects who progress to dementia would not benefit from treatment, the current protocol will exclude all subjects who have progressed to dementia.

Subjects who progress to dementia during this extension trial will be allowed to continue, since it is not known whether initiation of treatment at the prodromal stage would provide benefit to these subjects. Therefore, despite the lack of efficacy in the 017 population where treatment was initiated at the mild to moderate dementia stage, the sponsor believes that continued treatment of these subjects is warranted.

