### **5.1.3 Subject Exclusion Criteria**

The subject must be excluded from participating in the trial if the subject:

1. Has progressed to dementia due to AD per investigator diagnosis in the initial 104-week study.
2. Is in imminent risk of self harm, based on clinical interview or on the Columbia Suicidality Severity Rating Scale (C-SSRS), or of harm to others in the opinion of the investigator. Subjects who report suicidal ideation with intent, with or without a plan (e.g., suicidal ideation item 4 or 5 on the C-SSRS) in the past one (1) month or suicidal behavior in the past six (6) months should be excluded. Such subjects will be permitted to rescreen for entry into this study once in the Investigator's opinion, this risk of harm to self or others is no longer present.

3. Has developed a recent or ongoing, uncontrolled, clinically significant medical or psychiatric condition that precludes participation in this protocol in the judgment of the investigator.
4. Based on results from the EOT Visit (Visit 12) in the initial 104-week trial has results of clinical laboratory tests (complete blood count [CBC], blood chemistries, and urinalysis) that are clinically unacceptable to the investigator. However, it is recognized that lab results will not be available at Visit 12/12B if they occur on the same day. Therefore, such subjects may be enrolled prior to receiving these results; upon their receipt of the lab results, if the PI feels they are clinically unacceptable the subject should be discontinued.
5. Based on the results from the EOT Visit (Visit 12) has results of a physical examination, and vital signs that are clinically unacceptable to the investigator.
6. Has developed a form of dementia that is not Alzheimer's Disease, including but not limited to, dementia due to HIV infection, head trauma, vascular disease, Parkinson's disease, frontotemporal dementia, or Huntington's disease, as determined by the investigator.
7. Anticipates receiving any of the treatments listed in [Table 1](#) during the current trial.

Table 1 Prohibited Medications

Prohibited Medications, Supplements, and Other Substances
Anti-amyloid agents (e.g., tarenflurbil, tramiprosate)
Anti-amyloid antibodies (e.g., solanezumab)
Anti-amyloid vaccine (Subjects who received placebo only in a vaccine trial may participate in this trial.)

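### Part I dementia progressors have no Week 130 CDR-SB by rule, and no planned analysis varies the placebo/40 mg arm or isolates them, so the delayed-start difference could be attenuated unseen

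*Combined protocol and SAP*

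**What the plan says.** **Who can be measured.** Section 5.1.3 excludes a subject who "Has progressed to dementia due to AD per investigator diagnosis in the initial 104-week study". Section 2.1 says the same of progressors in every arm: they "will not be permitted to move into the long term extension study". Section 5.8 drops the retrieved-dropout follow-up used in Part I.

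**Why they are excluded.** Section 4.2.1.2 explains that the blind prevents excluding placebo progressors alone. It then excludes all progressors: "Given the concern that the placebo treated subjects who progress to dementia would not benefit from treatment".

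**Primary analysis.** Section 8.2.7.1 fits a longitudinal ANCOVA with categorical time and an unstructured covariance matrix. It uses all Part I data, "even that from subjects who do not continue into long term trial". Dementia status is not a model term.

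**Missing data.** Section 8.2.7.5 goes through reasons for discontinuation. On lack of efficacy it says "missing data caused by discontinuation due to lack of efficacy may belong to MAR because the discontinuation may depend on the observed efficacy outcomes". Ineligibility because of dementia is not mentioned. The tipping-point analysis shifts imputed values in the active arms only, "while the missing data in the control group are assumed to be the same as that obtained under MAR". The other two supportive analyses in Table 6 drop data after drug discontinuation or cholinesterase-inhibitor start, or fit a cLDA model to the MFAS.

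**The concern.** The disease course that the drug is meant to slow decides who is measured at Week 130. If MK-8931 delays dementia, more placebo than active subjects fall into the excluded group. That is a reasonable inference, but the documents give no progression rates.

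The model still makes an implicit statement about these subjects at Week 130. In the placebo arm, every Week 130 observation comes from a non-demented entrant who switched to 40 mg. MAR extends that post-switch course to demented subjects who never receive the drug, and whom Section 4.2.1.2 itself doubts would benefit. If they do worse than the model implies, the Pbo/40 mean at Week 130 is too favourable and the early-start advantage is understated.

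The Week 130 CDR-SB comparison is a primary objective (Section 3.1) and is meant to give supportive evidence of disease modification (Section 4.2.1.1). The tipping point starts from a significant result and asks how large a penalty on active removes it. It cannot show that a difference was attenuated because missing control values were worse than assumed.

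**Working it through.** **1. The plan's own figure.** Section 1.0 projects about 912 entrants. From Section 8.2.11.1.2: 1350 randomized × 0.75 (25% dropout at Week 104) × 0.90 (continuation) = 911.25; rounding up per arm, 304 × 3 = 912. The figure reproduces, with no visible separate allowance for the dementia exclusion. The share excluded is therefore an assumption below.

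**2. Scale of the effect.** Table 8 gives a 30-month mean change of +2.13 for Pbo/40 (higher is worse). The assumed Week 130 difference is not stated. A 30% effect would be 0.30 × 2.13 = 0.64 points. Working back from the 73.9% power in Table 9 gives about 0.69 points (SD 3.05 × √(1 − 0.359²) = 2.85; 450 × 0.63 = 283.5 per arm; two-sided α = 0.02495), or 0.62 if one-sided.

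**3. Simple formula.** If progressors are d points worse at Week 130 than MAR predicts, equally in both arms, then

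attenuation = d × (p_placebo − p_active) × 0.75,

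where p is the share progressing and 0.75 the share completing Part I. Assume p_active = 0.7 × p_placebo:

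| p placebo / p active | d = 0.5 | d = 1 | d = 2 |
|---|---|---|---|
| 0.10 / 0.07 | 0.011 | 0.023 | 0.045 |
| 0.20 / 0.14 | 0.023 | 0.045 | 0.090 |
| 0.30 / 0.21 | 0.034 | 0.068 | 0.135 |
| 0.40 / 0.28 | 0.045 | 0.090 | 0.180 |

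For example, 2 × (0.40 − 0.28) × 0.75 = 0.18 points. Only the excess between arms matters.

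**4. Simulation without a switch effect** (400,000 per arm). Assumed: 25% slowing; mean decline 2.13 on placebo; change proportional to (t/130)^1.3 plus noise of SD 0.8; diagnosis by logistic regression on Week 104 change with slope 1; 15%, 25% or 35% of placebo excluded. The estimate is a regression of Week 130 on earlier visits among entrants, applied to everyone.

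| Decline model | Extra decline in progressors | Attenuation |
|---|---|---|
| Normal, additive effect | 0 | 0% |
| Normal, additive effect | 1.0 to 1.5 points | about 5% to 13% |
| Gamma (shape 0.75), multiplicative, common slopes | 0 to 1.5 points | 12% to 32% |
| Same, slopes by arm | 0 to 1.5 points | 7% to 24% |

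With no extra decline the data are MAR by construction. The gamma attenuation in that case (12% to 21% with common slopes) is therefore model misspecification, not non-random missingness. Section 8.2.7.1 names a single unstructured matrix, which is closer to common slopes.

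**5. Second simulation, including the switch.** Assumed: 20% to 40% of placebo progressing and a 30% effect.

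- Diagnosis depends only on recorded CDR-SB: bias −0.003 to +0.004 points.
- Diagnosis also predicts later course: −0.03 to −0.07 points on a true difference of about 0.64.
- Non-progressing switchers gain 0.2 to 0.4 points and progressors gain nothing: −0.04 to −0.16 points. The true difference is itself smaller here, so the share runs from 0.042/0.476 = 9% to 0.155/0.406 = 38%.

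Every material bias runs toward no difference.

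**The case against.** The strongest reply is that the model is not blind to these subjects. Their CDR-SB scores, through Week 104 where observed, stay in the analysis, and this is the history on which MAR relies. If the diagnosis adds little to the recorded scores, the bias is close to zero, as steps 4 and 5 show for the linear case. The Cox analysis in Section 8.2.7.2 uses all Part I data, so differential progression is examined directly. There are no formal hypotheses, and Sections 8.2.7.1 and 8.2.11.1.2 already call Week 130 underpowered. A bias against the drug does not create a false claim of disease modification. All of this stands and limits the seriousness. It does not supply an analysis that varies Pbo/40 or isolates progressors.

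A reader might also infer more than the documents support:

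- *That nothing checks MAR.* The tipping point is a real check for non-random missingness. It covers active arms only.
- *That a bias of 12% or more is established.* That floor comes from one choice, skewed decline with common slopes; zero lies inside the plausible range.
- *That the planned treatment difference collapses.* In the gamma simulation the as-observed difference among entrants was −0.16 to −0.24 against a true −0.54 to −0.62. But Section 8.2.7.1 plans as-observed means and SDs only as basic summaries; treatment differences are model-based.
- *That no progressor can ever have a Week 130 value.* The exclusion came with this amendment, and the documents do not say whether progressors had already entered. Section 6.0 (footnote h) bars subjects whose AD progression the adjudication committee confirmed, while Section 7.1.2.3.1 provides for committee-judged progressors to enter when the investigator disagrees.

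**Conclusion.** The gap is real: an outcome-driven exclusion determines who has a Week 130 value, Section 8.2.7.5 does not address it, and no supportive analysis varies the Pbo/40 arm or treats progressors separately. The consequence is possible attenuation of the delayed-start difference, not a demonstrated bias.

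Without a switch effect, the size is about zero if the diagnosis reflects only recorded CDR-SB under a linear, normal model, about 5% to 13% with 1.0 to 1.5 points of unpredicted decline, and up to about 30% under skewed decline with common slopes. A switch benefit confined to non-progressors gives 0.04 to 0.16 points. Progression shares, excess decline and switch gains are all assumptions. With no formal hypotheses and a bias that runs against the drug, this is a worthwhile addition to the SAP. It is not a reason to reject the primary model.

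**What to change.** In Section 8.2.7.5:

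1. Define ineligibility because of AD dementia in Part I as its own missing-data pattern in every arm, and name Pbo/40 as the control arm.
2. Add one sensitivity analysis with the planned multiple-imputation code. Raise this pattern's imputed Week 130 CDR-SB over a grid, for example 0 to 1.5 points, with control and active shifts varied separately. Specify it as an addition: step c subtracts c, but a positive CDR-SB change is worsening (Table 8), so a literal subtraction would favour active, against that step's stated intent. State Week 130 as the timepoint, since step d gives 104 weeks as its example.
3. Tabulate by arm the number in this pattern and their last Part I CDR-SB.
4. Label as-observed Week 130 means as extension entrants only, and show them beside the same subjects' Week 104 means.

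Reconcile Section 6.0 (footnote h) and Section 7.1.2.3.1 on entry of committee-judged AD progressors, because that settles who falls in the pattern.

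The cost is SAP wording, a pattern flag and a rerun of existing code, with no new data. The downside is one more sensitivity table and possibly a wider reported range at Week 130.
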